5.2 Dose Interruption for Non-Hematopoietic Toxicity

In the event of CTC Grade 3 or 4 non-hematopoietic AE(s) that the investigator considers due to suspected disease progression, re-evaluation of tumor status is indicated, irrespective of scheduled clinic visits.

CTC Grade 3 or 4 believed to be drug related will be considered DLTs and will result in taking patients off study. One exception will be in the case of CTC Grade 3 diarrhea or Grade 3 nausea that is not attributed to hypercalcemia. In those situations ketoconazole may be resumed after a period of interruption that does not exceed 2 weeks with full antiemetics or antidiarrheal medication. In the event that these toxicities recur at grade 3 or greater, despite adequate supportive medications, this will be a DLT and the patients will be taken off study.

Ketoconazole may also be interrupted for a period that does not exceed 2 weeks in the event of symptomatic intolerable Grade 2 rash. At a minimum, reassessment of toxicity should be done twice weekly and more frequently if clinically indicated. When the AE decreases in severity to CTC Grade 1, the patient may resume the assigned dose.

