5.7 Hypercalcemia

A possible side effect of calcitriol is hypercalcemia; therefore all calcium levels used for the determination of toxicity will be corrected for serum albumin levels using the following formula:

$$Ca^{+2}_{cor} = Ca^{+2}_{ser} + (0.8)(4.0 - Alb_{ser})$$

Patients developing:

- a) Corrected serum calcium ≥ 12 mg/dl persisting ≥ 7 days or
- b) Any corrected calcium ≥ 13 mg/dl with symptoms secondary to hypercalcemia
or
- c) Any corrected serum calcium ≥ 14 mg/dl

Calcitriol will be stopped and calcium level will be repeated in 1 week. Treatment will resume when calcium level returns to ≤ 10.5 mg/dl. Recovery from hypercalcemia must occur within 2

weeks to continuation on study. If this toxicity recurs, the patient will be taken off study. Further therapy off study would then be at the discretion of the treating physician.

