5.10 Criteria for Discontinuation

Patients may be discontinued from trial treatment and assessments at any time at the discretion of the investigator(s). Specific reasons for discontinuing a patient from this trial are the following:

- Disease progression
- Intercurrent illness that prevents further administration of treatment
- Unacceptable AE
- Patient develops kidney stones
- Patient decides to withdraw from the study
- General or specific changes in the patient's condition render the patient unacceptable for further treatment in the judgment of the investigator

PSA progression is an increase of 50% above the nadir at a minimum of 5 ng/mL. (i.e. PSA must rise a minimum of 5 units)

If that criterion is reached patients will be declared to have PSA Progressive Disease (PD), **but:**

- a. If radiographs do not confirm PD
- b. PSA and symptoms are stable or improved from baseline
- c. Patient is in agreement

Investigator will have the discretion to continue investigational therapy until:

PSA achieves a level of $> 50\%$ of baseline

or

Radiographic or symptomatic PD

or

Patient wish to discontinue

The two options for categorizing withdrawal are either progressive disease (PD) or an AE (>1AE may be documented as a reason for withdrawal). Only 1 event will be captured as the cause of death. Note that death is an outcome and not an AE.

All trial treatment-related toxicities and SAEs must be followed up until resolution.

All patients who have new or worsening CTC Grade 3 or 4 laboratory values at the time of withdrawal must have further tests performed, and the results must be recorded appropriately. Until the laboratory values have returned to CTC Grade 1 or 2, unless these values are not likely to improve because of the underlying disease. In these cases, the investigators must record their opinions in the patients' medical records. Laboratory abnormalities should **not** be reported as AEs unless any criterion for a SAE is fulfilled, the laboratory abnormality causes the patient to discontinue from the study, or the investigator insists the abnormality should be reported as an AE.

At withdrawal all ongoing study-related toxicities and SAEs must be followed until resolution, unless in the investigator's opinion, the condition is unlikely to resolve due to the patient's underlying disease.

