9.0 SAFETY EVALUATION

9.1 Adverse Events

9.1.1 Definitions

An adverse event or adverse experience (AE) is any untoward medical occurrence associated with the use of a drug in humans, whether or not considered drug related. Therefore, an AE can be ANY unfavorable and unintended sign (including an abnormal laboratory finding), symptom, or disease temporally associated with the use of a medicinal (investigational) product, whether or not considered related to the medicinal (investigational) product (attribution of ‘unrelated’, ‘unlikely’, ‘possible’, ‘probable’, or ‘definite’).

An AE is considered “unexpected” if it is not listed in the investigator brochure or is not listed at the specificity or severity that has been observed; or if an investigator brochure is not required or available, is not consistent with the risk information described in the general investigational plan in other study-related documents.

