11.1.1.3 Abnormal Normal Laboratory Values

Only clinically significant laboratory abnormalities that require active management will be recorded as AEs or SAEs on the CRF (e.g., abnormalities that require study drug dose modification, discontinuation of study treatment, more frequent follow-up assessments, further diagnostic investigation, etc.).

If the clinically significant laboratory abnormality is a sign of a disease or syndrome (e.g., alkaline phosphatase and bilirubin 5 x the upper limit of normal associated with cholecystitis), only the diagnosis (e.g., cholecystitis) needs to be recorded on the Adverse Event CRF.

If the clinically significant laboratory abnormality is not a sign of a disease or syndrome, the abnormality itself should be recorded as an AE or SAE on the CRF. If the laboratory abnormality can be characterized by a precise clinical term, the clinical term should be recorded as the AE or SAE. For example, an elevated serum potassium level of 7 mEq/L should be recorded as “hyperkalemia”

Observations of the same clinically significant laboratory abnormality from visit to visit should not be repeatedly recorded as AEs or SAEs on the CRF, unless their severity, seriousness, or etiology changes.

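### Section 5.7(a) stops calcitriol for calcium that stays high for 7 days, but no blood draw is assigned to show it; a minor conflict on recording laboratory AEs sits in 5.10

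*Combined protocol and SAP*

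**What the plan says.** **Calcium and creatinine rules.** Section 5.7 has three triggers for stopping calcitriol, all on albumin-corrected calcium: (a) "Corrected serum calcium ≥ 12 mg/dl persisting ≥ 7 days"; (b) 13 mg/dl or more with symptoms; (c) 14 mg/dl or more regardless of symptoms. Once a trigger is met, "Calcitriol will be stopped and calcium level will be repeated in 1 week. Treatment will resume when calcium level returns to" a value of 10.5 mg/dl or less. Section 5.8 withholds calcitriol at a creatinine of 2 mg/dL and removes the patient if 2.5 mg/dL or more is sustained beyond 72 hours. The section 7.0 calendar and its footnote a place calcium, albumin and creatinine at weeks 5 and 9 and every 4 weeks after that. Under 5.2, "CTC Grade 3 or 4 believed to be drug related will be considered DLTs and will result in taking patients off study", with an exception for some diarrhea and nausea.

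**Recording rules.** Section 5.10 says that abnormal laboratory values are not to "be reported as AEs unless any criterion for a SAE is fulfilled, the laboratory abnormality causes the patient to discontinue from the study"; its third exception reads "or the investigator insists the abnormality should be reported as an AE". The same paragraph opens with: "All patients who have new or worsening CTC Grade 3 or 4 laboratory values at the time of withdrawal must have further tests performed". Section 11.1.1.3 states: "Only clinically significant laboratory abnormalities that require active management will be recorded as AEs or SAEs on the CRF", and gives dose modification and closer follow-up as examples of such management. Section 9.1.1 says "an AE can be ANY unfavorable and unintended sign (including an abnormal laboratory finding". Section 12.2 grades and tabulates toxicity and counts every treated patient as evaluable, without naming the data source.

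**The concern.** A stopping rule that needs a value to persist can only work if someone is told to take the second sample. In 5.7 the 1-week repeat follows the stop, so it serves recovery and cannot establish the 7 days that limb (a) requires. Until a second sample is taken, limb (a) cannot be shown to be met and dosing continues. Section 6.4.1 names hypercalcemia first among the common effects of high-dose calcitriol, and the regimen adds ketoconazole in order to slow calcitriol breakdown.

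The lesser concern is the AE record. Taken as a general rule, the 5.10 sentence keeps out some episodes that 11.1.1.3 would record, and nothing says which rule prevails. Toxicity and tolerability are a secondary objective, so the tabulated result could depend on which section the coordinator follows.

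**Working it through.** The plan gives no figure on this point, so there is none to reproduce. The check compares the sections and counts doses.

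**1. Which calcium values depend on limb (a).** Limb (c) catches 14 mg/dl or more, and limb (b) catches 13 mg/dl or more with symptoms. An asymptomatic first value of 12 to below 14 mg/dl falls under neither. Some of these may leave the study under 5.2 as drug-related Grade 3 or 4. The documents do not print the CTCAE calcium cut-offs, so I have not computed that share.

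**2. Can the calendar show 7-day persistence?** Scheduled draws are 28 days apart (day 29, day 57, and so on). With random onset, a 7-day episode meets one scheduled draw with probability 7/28 = 25% and two with probability 0. Two consecutive scheduled draws can show only about 28 days.

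**3. Doses given meanwhile.** Calcitriol is 10 mcg on the first three days of each week (sections 4.1 and 7.0).
- High value on day 29, next scheduled draw on day 57: days 29–31, 36–38, 43–45 and 50–52, so 4 × 3 = 12 doses, or 12 × 10 = 120 mcg.
- With a repeat on day 36 before dosing: days 29–31, so 3 doses, or 30 mcg.
- Difference: 9 doses, or 90 mcg. Any 28-day interval contains 12 dosing days and any 7-day interval contains 3, so the count does not depend on the weekday of the visit.

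**4. Creatinine.** Section 5.8 withholds on a single value, so the hold has no such gap. Only the sample that would establish the 72-hour removal rule is unstated.

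**5. What the 5.10 sentence could leave out, if read generally.** Serious events meet its first exception. Drug-related Grade 3 or 4 events go off study under 5.2 and meet its second. Symptoms under limb (b) are reportable in their own right. What remains is non-serious, asymptomatic episodes, below Grade 3 or judged unrelated, that interrupt calcitriol and recover. For calcium, 5.7 already bases toxicity on corrected laboratory levels. The remainder is therefore mainly creatinine: inclusion criterion 10 admits up to 2 mg/dL and 5.8 holds at 2 mg/dL, so a rise from 1.9 to 2.0 is enough.

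**6. Illustration of size for step 5.** The number of episodes is not known. If k of 15 patients had one, exact (Clopper-Pearson) 95% intervals are:
- k = 0: 0% (0–21.8)
- k = 1: 6.7% (0.2–31.9)
- k = 2: 13.3% (1.7–40.5)
- k = 3: 20.0% (4.3–48.1)

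Under 11.1.1.3 the k row applies. Under 5.10 read generally, the result could be as low as the k = 0 row if the investigator never insists. If 12.2 uses laboratory values, the difference is zero.

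The range 0 to 3 is an assumption. Its only anchors are earlier trials without ketoconazole: no hypercalcemia-driven dose reduction in 43 patients (section 2.3.1) and no hypercalcemia in the paclitaxel trial (section 2.3.3; 36 patients, 26 with pharmacokinetics). The upper limit for zero events, 1 − 0.025^(1/n), is 8.2%, 9.7% and 13.2% for n = 43, 36 and 26. Multiplied by 15, that is 1.2, 1.5 and 2.0 patients. Those events are broader than the set in step 5 and say nothing about creatinine.

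**The case against.** **On 5.7.** A rule that speaks of persistence implies a second value. Extra draws are not prohibited, 11.1.1.3 contemplates more frequent follow-up of abnormal results, and 5.10 lets the investigator discontinue a patient at any time. Most clinicians would repeat a calcium of 12 mg/dl. That stands, and it is why 12 doses is an upper figure, not an expected one. A reader might infer that patients will go a month on high calcium; the documents do not support that. They do leave the stopping rule dependent on a sample that no section assigns. The twice-weekly reassessment in 5.2 does not fill the gap: it sits in the paragraph on ketoconazole interruption for rash and names no blood test.

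**On 5.10.** The sentence lies in the discontinuation section, between text about values at withdrawal and follow-up after it, while recording has its own titled rule in 11.1.1.3. Reading it as limited to withdrawal is natural and removes the conflict. Even read generally, the investigator may insist on reporting. A rise from 1.9 to 2.0 mg/dL must also be judged clinically significant before 11.1.1.3 records it. All of this stands and makes the point minor. It does not dispose of it, because the sentence carries no time limit of its own and, read generally, it also cuts across Table 2 of 9.1.3, which reports Grade 1–2 events at least possibly related to treatment.

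A reader might also infer that hypercalcemia will disappear from the safety results. The documents point the other way: 5.7 determines calcium toxicity from corrected laboratory levels, and 12.2 makes every treated patient evaluable. That 12.2 names no data source is missing detail, not an error in itself.

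**Conclusion.** The 5.7 gap holds and is the part worth acting on. As written, limb (a) cannot be tested from the scheduled samples in time. For an asymptomatic first value of 12 to below 14 mg/dl not removed under 5.2, up to 12 doses (120 mcg) can precede the next scheduled draw, against 3 (30 mcg) with a 7-day repeat. This assumes no unscheduled draw and uninterrupted dosing. How many patients would enter that range is unknown.

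The 5.10 point holds only if the sentence is not confined to withdrawal. It then concerns a small set of non-serious, recovered episodes, mainly creatinine holds, which may be empty. The rates in step 6 of the working are illustrations on an assumed 0 to 3 episodes, not estimates. PSA response and the go/no-go rule are unaffected by either part.

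**What to change.** 1. **Section 5.7.** After any first corrected calcium of 12 mg/dl or more that does not already stop treatment, repeat calcium and albumin 7 days later, before the first calcitriol dose of the following week, and stop calcitriol if the corrected value is still 12 mg/dl or more. These two timings coincide when the first sample is taken on the first day of a treatment week. If it is taken later in the week, the following week's doses should wait for the repeat result.
2. **Section 5.8.** Repeat creatinine just after 72 hours following any value of 2.5 mg/dL or more.
3. **Section 5.10.** Delete the sentence on reporting laboratory abnormalities, or limit it expressly to incidental values at withdrawal, so that 11.1.1.3 governs episodes during treatment.
4. **Section 12.2.** Tabulate worst-grade corrected calcium and worst-grade creatinine from laboratory values for every treated patient, whatever was entered as an AE.

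The cost is wording in four sections, one table from values already collected, and an occasional unscheduled routine blood draw for a patient who crosses a threshold. Sample size and the regular calendar do not change.

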6.0 AGENT FORMULATION AND PROCUREMENT

6.1 Ketoconazole

Ketoconazole will be obtained from commercial sources and provided by third party or patient resources.

Ketoconazole Formulation				
Treatment	Strength	Description	Daily dose	Tablets per dose
Ketoconazole	200-mg tablet	Ketoconazole is a white to slightly beige, odorless powder, soluble in acids, with a molecular weight of 531.44.	1200 mg	2 tablets TID

Ketoconazole is available under the brand name Nizoral^R. It is available generically as ketoconazole.

Ketoconazole treatment will be taken 3 times per day (e.g. with meals), every day about the same time. It can be taken with or without food. If a patient forgets to take a dose, he should take the last missed dose as soon as they remember. However, do not double dose if it is time for the next dose.

6.1.1 Storage

Ketoconazole should be stored at room temperature between 15 and 30°C (59 and 86°F). Protect from moisture.

6.2 Calcitriol

Calcitriol will be provided to the study subjects by study staff. 0.5 mcg caplets will be employed. Our ISCI investigational pharmacist will order the calcitriol and distribute it as investigational for this study. The pharmacist will follow all GCP for tracking, maintaining and distributing the calcitriol as investigational in this study.

6.2.1 Storage

Please refer to the Complete Product Information.

6.3 Hydrocortisone

Hydrocortisone is available commercially in 5, 10, 25 and 50 mg tablets and will be obtained from commercial sources and provided by third party or patient resources

Please refer to the complete product information.

6.4 Expected Toxicities

6.4.1 Calcitriol

Commonly seen side effects with high dose calcitriol include hypercalcemia, hypercalciuria, and hyperphosphatemia. Clinical toxicity has been mostly linked to the level and duration of associated hypercalcemia. Early signs of hypercalcemia include weakness, headache, somnolence, nausea, vomiting, dry mouth, constipation, muscle pain, bone pain, metallic taste, and anorexia.

Late signs include polyuria, polydipsia, anorexia, weight loss, nocturia, conjunctivitis (calcific), pancreatitis, photophobia, rhinorrhea, pruritis, hyperthermia, decreased libido, elevated blood urea nitrogen (BUN), albuminuria, hypercholesterolemia, elevated aspartate transaminase (AST) and alanine transaminase (ALT), ectopic calcification, nephrocalcinosis, hypertension, cardiac arrhythmias, dystrophy, sensory disturbances, dehydration, apathy, arrested growth, urinary tract infections, and, rarely, overt psychosis. Chronic hypercalcemia has also been associated with an increase in creatinine levels in patients with normal baseline renal function.

Hypersensitivity reactions to calcitriol are rare but have been reported. One case of allergic reaction and another case of erythema multiforme have been confirmed by rechallenge (Rocaltrol® Complete Product Information).

6.4.2 Ketoconazole

Ketoconazole is one of a series of imidazoles which are active antifungal agents; ketoconazole at a dose of 200mg daily is widely used in the therapy of cutaneous, esophageal and urinary tract fungal infections and at 400mg TID is frequently prescribed in the therapy of androgen independent prostate cancer (with glucocorticoids to prevent adrenal insufficiency)

Ketoconazole mechanism of antifungal and perhaps antitumor action depends on its ability to inhibit numerous cytochrome P450 enzymes, disrupting membrane lipid structure as well as modifying the activity of a number of other intracellular compounds: vitamin D, retinoids. Ketoconazole has demonstrated a broad range of antitumor effects in preclinical systems (in vitro), but has not been widely tested in the active therapy of any cancer other than prostate cancer, where its activity was originally believed to depend on disruption of androgen signaling. Ketoconazole is generally a well tolerated agent. The major toxicities are GI (nausea, vomiting, hepatotoxicity) constitutional toxicities (headache, dizziness, rash, lethargy, dry skin, pruritis, somnolence, diarrhea) and rare myelosuppression and anaphylaxis.

6.4.3 Hydrocortisone

Adverse reactions to hydrocortisone are those associated with glucocorticoid and mineralocorticoid use. Most occur with prolonged and high dose therapy and are somewhat reduced in patients receiving alternate day therapy where suppression of endogenous adrenal steroid production is reduced. The hydrocortisone dose in this trial is intended as glucocorticoid replacement and is anticipated to have limited potential to cause any of the following side effects: electrolyte disturbances, fluid retention, and exacerbation of congestive heart failure increased risk of infection (esp. mucocutaneous candidiasis), polyuria, fluid retention, “moon faces”, centripetal obesity, mood alterations (depression or anxiety). Long term use may cause myopathy, osteoporosis, impaired wound healing, fragile skin, and Cushingoid habitus. Patients with mild glucose intolerance may develop frank diabetes, and glaucoma can be precipitated in patients with increased intraocular pressure. Mood disturbances and increased appetite are also commonly reported. This drug must not be abruptly discontinued following prolonged usage since adrenal insufficiency is common.

7.0 STUDY CALENDAR

Baseline evaluations are to be conducted within 28 days prior to start of protocol therapy. Radiographs must be done within 6 weeks of entering the study.

		Cycle 1				Cycle 2				Cycle 3				Cycles 4+	Off Study
	Pre-Study (-28 to -1 days)	Wk 1	Wk 2	Wk 3	Wk 4	Wk 5	Wk 6	Wk 7	Wk 8	Wk 9	Wk 10	Wk 11	Wk 12		
Ketoconazole		X	X	X	X	X	X	X	X	X	X	X	X	Weekly	
Calcitriol		X	X	X	X	X	X	X	X	X	X	X	X	Weekly	
Hydrocortisone		X	X	X	X	X	X	X	X	X	X	X	X	Weekly	
Informed consent	X														
Demographics	X														
Concurrent meds	X					X				X				Every 4 wks	
Medical history	X													Every 4 wks	X
Physical exam, Vital Signs, Weight	X					X				X				Every 4 wks	X
CBC w/diff, plts	X					X				X				Every 4 wks	X
Serum chemistry ^a	X					X				X				Every 4 wks	X
Adverse event evaluation						X				X				Every 4 wks	
Performance status	X					X				X				Every 4 wks	X
PSA	X					X				X				Every 4 wks	
Tumor measurements	X	Tumor measurements are repeated every 4-12 weeks (measurable disease). Documentation (radiologic) must be provided for patients removed from study for progressive disease.													X ^c
Radiologic evaluation ^b	X	Radiologic measurements should be performed every 12 weeks from the start of calcitriol													X ^c

Ketoconazole: 400 mg given TID starting D 1 (except if participating in the PK portion begin day 4)

Calcitriol: 10 mcg; Calcitriol will be given for 3 consecutive days starting the 1st day of each week, day 1,2,3,8,9,10,15,16,17

Hydrocortisone: will be given 20mg AM, 10mg PM in the evening starting the day before the first dose of calcitriol

a--Alkaline phosphatase, total bilirubin, LDH, total protein, SGOT(AST), SGPT(ALT) will be obtained monthly. Albumin, Bicarbonate, BUN, calcium, chloride, creatinine, glucose, total protein, and phosphorous will be obtained monthly.

b- Every 12 weeks in patients with measurable disease. Every 12 weeks in the absence of measurable disease.

c- If partial or complete response are assessed, repeat in 1 month for confirmation. Longer intervals as determined by the study protocol may also be appropriate.

8.0 MEASUREMENT OF EFFECT

8.1 RECIST

The modified Response Evaluation Criteria in Solid Tumors (RECIST) and Recommended NCI PSA Response Criteria will be used for this trial for objective tumor response assessment. The primary response objective of this trial is the PSA response rate. In patients with measurable disease CR and PR will be assessed by RECIST criteria. Measurable response is a secondary objective of the phase II portion of this study.

Overall responses for all possible combinations of tumor responses in target and nontarget lesions with or without the appearance of new lesions*

Target lesions	Nontarget lesions	New lesions	Overall response
CR	CR	No	CR
CR	Incomplete response/SD	No	PR
PR	Non-PD	No	PR
SD	Non-PD	No	SD
PD	Any	Yes or no	PD
Any	PD	Yes or no	PD
Any	Any	Yes	PD

CR = complete response; PR = partial response; SD = stable disease; and PD = progressive disease. See Appendix B for more details.

Responses should be confirmed at a follow-up visit at least 4 weeks later

